50%	Degarelix + BSC	64	72	84
	Placebo + BSC	32	36	42
	Total	96	108	126

Duration of Study and Number of Participating Sites

To estimate the expected study duration and resources, we assume that the recruitment rate will be half of what we anticipate. Under this assumption, various scenarios were examined in order to identify an optimal combination between the number of sites, the study duration (which includes recruitment period and follow-up period) and the estimated budget. The study will include four VA medical centers and each center will randomize 17 patients per month on average; however, estimated recruitment rate will vary depending on the patient volume of each participating center as the disease evolves. Based on these assumptions, the recruitment period was found to be approximately three

months. This will be followed by approximately one month of follow up for the last patients randomized into the study followed by one month of data analysis. Thus, the study duration including start-up will be approximately five months.

Interim Analysis and Criteria for Study Termination

A mid-term interim analysis of the primary endpoint will be performed at half of the patients or 99 randomized patients complete or are terminated the study. If the mid-term analysis of the primary endpoint indicates that the null hypothesis can be rejected with a boundary value of 2.77 (standardized $Z > 2.77$ or < -2.77) at an α -level of 0.006 or accepted with a boundary value of 0.44 ($-0.44 \leq \text{standardized } Z \leq 0.44$) based on O'Brien and Fleming criteria, the study will be recommended for trial termination for efficacy and futility reasons (shown in the Figure 1). Enrollment will be paused if the interim analysis results indicate crossing of the threshold for futility or efficacy until the final DMC recommendation is rendered.

Meanwhile, the drug toxicity will be closely monitored and analyzed. As described in previous sections, arrhythmia and thromboembolic complications are adverse events of special interest that will be monitored closely and graded according to on CTCAE 5.0. Once the toxicity markers reach a threshold of 25% (Ray and Rai 2011), a statistical analysis of the toxicity will be performed. If the experimental (degarelix) group has a significant higher toxicity compared to the placebo group at an α -level of 0.01, then results will be reported to the DMC for a recommendation for trial termination.

[figure not shown]

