## 1.0 SUMMARY

The overall goal of the proposed study is to determine whether if temporary androgen suppression improves the clinical outcomes of Veterans who are hospitalized to an acute care ward due to COVID-19. This study will compare degarelix + best supportive care (BSC) to placebo + BSC for the participants' clinical improvement. The study will randomize 198 patients from four participating VA sites (another four backup sites) over a 90-day recruitment period. The primary end point of the study is a composite endpoint of mortality, ongoing need for hospitalization, or requirement for mechanical ventilation/extracorporeal membrane oxygenation (ECMO) at 15 days after the randomization. The study hypothesis is that the degarelix treatment group will reduce the event rate of the composite primary endpoint. Secondary objectives of this study include: 1). the composite endpoint of mortality, ongoing need for hospitalization, or requirement for mechanical ventilation/extracorporeal membrane oxygenation (ECMO) at 30 days after the randomization.2). time to clinical improvement as defined by a decline of 2 categories or more from the baseline on the modified 7-category ordinal scale of clinical status of hospitalized influenza patients (influenza scale, see Appendix 5.1) or hospital discharge, 3). inpatient mortality, 4). duration of hospitalization, 5). duration of intubation for mechanical ventilation, 6). time to normal temperature ( $T < 37.5^{\circ}\text{C}$  for  $\geq 48$  hours), and 7). maximum severity of COVID-19 illness based on the influenza severity scale.

This statistical analysis plan (SAP) is drafted after review of the current HITCH study protocol and case report forms (CRFs), but before any analysis of the data has begun. Detailed information is given to aid in the production of the statistical output and the statistical section of the final study report, and potential manuscripts for publication. This document provides background of the study based on the protocol and describes the populations that will be analyzed. All participant characteristics and the efficacy and safety parameters that will be evaluated, along with the specific statistical methods, are described. The SAP is an independent statistical document in accordance to the updated version of the study protocol and it serves the guideline for the statistical analyses of the data collected during the study.

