## 2.6 Sample Size Consideration

In a recent antiviral drug trial to treat adults hospitalized with severe COVID-19 published in the New England Journal of Medicine (NEJM) on March 18, 2020^32, the results showed that a mortality rate of 17%, hospital stay rate of 50%, and ECMO or mechanical intubation rate of 11% among the patients managed with BSC after two-week follow-up. In the current study, we propose a composite endpoint of mortality, ongoing need for hospitalization, and ECMO or mechanical intubation at 15 days after randomization. We are expecting to reduce the composite endpoint rate to 35% after the degarelix treatment plus BSC from 60% for patients treated placebo plus BSC.

The sample size estimation and power analysis shown in Table 2 are based on the hypothesis testing of the primary endpoint, which is the composite endpoint of mortality, hospital stay rate, and ECMO or mechanical intubation at 15 days after

randomization (Day 15). According to the composite endpoint outlined in the previous section, we assume that an effect size for the primary endpoint of 42% can be anticipated in the degarelix group. The other assumptions include a three-month accrual time and one-month follow-up time, and 2:1 sample allocation of degarelix: placebo treatment group. The sample size for the study is estimated based on a superiority trial design. To have 90% power of detecting the expected 42% reduction using a two-sided two proportion test with a significance level of 0.05 in the degarelix compared to the placebo group will require 186 evaluable patients total (i.e. 124 evaluable patients in the degarelix group and 62 evaluable patients in the placebo group). Based on an assumed 5% attrition rate, 198 patients will be required (i.e. 132 in the degarelix group and 66 in the placebo group) to achieve actual statistical significance at alpha level of 0.05 and power of 90% (Appendix 5.5).

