## 3.9 Interim Analyses

A mid-term interim analysis of the primary endpoint will be performed when half of the participants (99 randomized participants) complete or are terminated from the study. If the mid-term analysis of the primary endpoint indicates that the null hypothesis can be rejected with a boundary value of 2.77 (standardized  $Z > 2.77$  or  $< -2.77$ ) at an  $\alpha$ -level of 0.006 or accepted with a boundary value of 0.44 ( $-0.44 \leq \text{standardized } Z \leq 0.44$ ) based on O'Brien and Fleming criteria, the study will be recommended for trial termination for efficacy and futility reasons (shown in Appendix 5.7). The number and percentage of participants with the composite endpoint at day 15 will be summarized and compared using Pearson  $\chi^2$  test (Table 3.9.1a) using SAS PROC FREQ. For

logistic regression analysis, if the coefficient for treatment effect is significant (i.e., the confidence interval for the odds ratio does not include 1), then the null hypothesis will be rejected. The significant level for each covariate coefficient in the model will best determined by Wald test (Table 3.9.1b) using SAS RPOC LOGISTIC. The analysis will be done in the ITT population. The detailed analysis is described in the primary endpoint analysis in the section 3.7.1.

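### The interim futility region is a symmetric band around zero, so a neutral result triggers a stop recommendation but a moderately harmful one crosses no boundary

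*SAP*

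**What the plan says.** SAP 3.9 and Protocol section 10 (Interim Analysis and Criteria for Study Termination) give the same rule. The interim takes place when "half of the participants (99 randomized participants) complete or are terminated from the study". The null hypothesis is "rejected with a boundary value of 2.77" (Z above 2.77 or below -2.77, nominal alpha 0.006) or "accepted with a boundary value of 0.44" (Z from -0.44 to 0.44 inclusive). If either happens, "the study will be recommended for trial termination for efficacy and futility reasons". Neither document states an action for 0.44 < |Z| ≤ 2.77 on either side, so the trial goes on there. The protocol adds: "Enrollment will be paused if the interim analysis results indicate crossing of the threshold for futility or efficacy".

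The aim has one direction. SAP 1.0 says: "The study hypothesis is that the degarelix treatment group will reduce the event rate of the composite primary endpoint". The test has two: SAP 2.6 sizes the trial for "detecting the expected 42% reduction using a two-sided two proportion test with a significance level of 0.05".

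The only other numerical rule (Protocol section 10, SAP 3.8.2) concerns arrhythmia and thromboembolic events: a 25% trigger, then a comparison at alpha 0.01. It does not look at the composite of death, ventilation or ECMO, and continued hospitalisation.

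**The concern.** A futility rule should stop a trial when the effect it was built to show has become implausible. The further the interim result falls on the wrong side of zero, the stronger that case becomes. Here the order is reversed. Zero difference prompts a stop recommendation; a result showing degarelix patients doing worse does not, until it is extreme. Even beyond -2.77 the rule's wording names only efficacy and futility, so a strongly harmful result has no label of its own.

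At stake is what the written rule tells the DMC. On a moderately harmful trend in the primary endpoint, it reports that no boundary was crossed. If enrolment is still open, randomisation then continues 2:1 towards the arm that is doing worse, with little chance of showing benefit.

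**Working it through.** **Inputs.** Boundaries 2.77 and 0.44 at 99 of 198 patients (SAP 3.9). Allocation 2:1, so 66 degarelix and 33 placebo at the interim. Rates 60% placebo and 35% degarelix (SAP 2.6). Final alpha 0.044, critical value 2.014 (SAP 3.7.1). The plan does not state the sign of Z; positive is taken here as favouring degarelix. The rule is symmetric, so the choice does not matter.

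**1. The plan's own boundaries.** Take a two-sided O'Brien-Fleming-shaped design with an inner acceptance wedge (Pampallona-Tsiatis form): two looks, half information, alpha 0.05 two-sided, power 0.90, binding futility. The solved constants are C1 = 1.958 and C2 = 1.338.
- Rejection: C1/√0.5 = 2.769.
- Acceptance: (C1 + C2)√0.5 - C2/√0.5 = 2.330 - 1.892 = 0.438.

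These match 2.77 and 0.44. The two-sided p at 2.77 is 0.0056, which rounds to 0.006.

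**2. What the rule does to real counts.** Pooled Z = (p_plac - p_deg)/√[p̄(1 - p̄)(1/66 + 1/33)]. With placebo 20/33 (60.6%):

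| Degarelix | Rate | Excess (points) | Z | Rule |
|---|---|---|---|---|
| 40/66 | 60.6% | 0 | 0 | stop |
| 42/66 | 63.6% | 3.0 | -0.294 | stop |
| 43/66 | 65.2% | 4.5 | -0.443 | continue |
| 56/66 | 84.8% | 24.2 | -2.69 | continue |
| 57/66 | 86.4% | 25.8 | -2.91 | stop |

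At exactly 60% on placebo, 85% on degarelix gives Z = -2.772, just over the boundary. The zone therefore runs from about 5 to just under 25 points.

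**3. How often the zone is entered.** Exact binomial enumeration at 66 and 33, placebo 60%. The degarelix rates above 60% are assumptions.

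| True degarelix rate | Harmful, continues | Neutral band, stops | Z < -2.77, stops |
|---|---|---|---|
| 60% | 32% | 35% | 0.3% |
| 65% | 51% | 29% | 1.3% |
| 70% | 68% | 20% | 4.4% |
| 75% | 74% | 10% | 12% |

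At 70% the rule stops in about 24% of trials (19.6% + 4.4%). In the remaining 8.5% it continues from the favourable side.

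**4. Chance of a final benefit finding.** Design drift at 132 and 66 = 0.25/√(0.35×0.65/132 + 0.60×0.40/66) = 3.415. Conditional power at half information = 1 - Φ[(2.014 - z√0.5 - 3.415×0.5)/√0.5].
- z = +0.44: 1 - Φ(-0.006) = 50% (stops)
- z = 0: 1 - Φ(0.434) = 33% (stops)
- z = -0.45: 1 - Φ(0.884) = 19% (continues)
- z = -1: 1 - Φ(1.434) = 7.6% (continues)
- z = -2: 1 - Φ(2.434) = 0.75% (continues)

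If the interim trend persists instead, the figure is below 0.01% throughout the harmful zone.

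**5. Cost of closing the zone.** At 35% against 60%, P(Z < -0.44) = 0.21%, which caps the loss of power. A bivariate normal calculation gives power of 91.18% with the band and 91.16% with a one-sided region. Type I error in the benefit direction is 2.22% under both.

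**The case against.** Three things can be said for the plan, and each stands in part.

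First, the design is a recognised one. The boundaries reproduce, all tests are two-sided, the null is an odds ratio of one, and Protocol section 10 promises a confidence interval that informs in either direction. A reader might infer that the boundaries are miscalculated; step 1 shows that they are not. But no stated objective is to establish harm, and the coherence of a two-sided wedge does not make it suit a benefit-only hypothesis.

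Second, the written boundary is not the only protection. A reader might infer that the trial has no monitoring for harm on death or prolonged stay. The documents do not support that. Death, life-threatening events and prolonged hospitalisation are SAEs (Protocol section 8). The DMC receives all SAEs whether related or not, decides when to be unblinded, can advise stopping for safety, and makes early-termination determinations (Protocol sections 8, 9 and 12). The gap is in the pre-specified boundary.

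Third, a reader might infer that patients would certainly go on being randomised to the worse arm. That depends on when 99 patients have completed. At 198 patients in 90 days the 99th is randomised near day 45. If completion means the Day 60 follow-up in Protocol section 5, the interim falls near day 105, after planned enrolment ends. If completion means death or discharge, as SAP 2.3 has it in one place, it could come earlier. The protocol's pause rule assumes that enrolment is still open, but the documents do not settle it.

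A reader might also put the upper edge of the zone near 29 points by multiplying 2.77 by a fixed standard error of about 0.104. The pooled standard error shrinks as the degarelix rate rises, so the zone ends just under 25.

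**Conclusion.** The point holds as a mismatch between the futility region and the trial's question. Followed as written, the rule recommends stopping where the chance of showing benefit is 33% to 50% (Z from 0 to +0.44) and continues where it is 19% or less (Z below -0.44). The uncovered zone is a degarelix rate about 5 to just under 25 points above a 60% placebo rate. It is entered in about 68% of trials if the true degarelix rate is 70%, and about 74% if it is 75%.

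These figures rest on a 66:33 split at the interim, the plan's 60% placebo rate, assumed harmful degarelix rates, and a final critical value of 2.014. The boundary figures (Protocol Figure 1, SAP Appendix 5.7) are not available here, so how they draw the regions is unchecked. The change is worth making before the interim because it is nearly free; it does not rest on any claim that the DMC would be unable to act.

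**What to change.** In SAP 3.9 and Protocol section 10, and in the boundary figures if they show the same band:
- define Z so that positive values favour degarelix;
- keep Z > 2.77 as the efficacy boundary;
- recommend stopping for futility at any Z ≤ 0.44;
- state that Z < -2.77, which lies inside that region, is to be reported as evidence of harm and not as efficacy.

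State also what counts as completing for the 99 patients, so that it is clear whether enrolment will be open at the interim.

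Cost: at most 0.2 points of power at 35% against 60%. Type I error cannot rise, because the change only adds stops without rejection. Futility stops under no effect go from about 34-35% to about 67%. At an assumed 70% on degarelix they go from about 20-22% to about 92%. The real concession is a formal final test of harm after such a stop. Under the current rule that test would be significant for harm in about 22% of trials at a true 70% and 43% at a true 75%. The estimate and confidence interval can still be reported after stopping.

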The primary study endpoint will be the composite outcome of mortality, ongoing need for hospitalization, and ECMO or mechanical intubation at 15 days after randomization. This outcome will be compared according to assigned treatment groups, using Pearson χ^2 test. The test for differences between the treatment groups in the primary outcome will be conducted at an overall α -level of 0.05 (i.e. $\alpha = 0.006$ for mid-term interim analysis, $\alpha = 0.044$ for the final analysis). If a patient drops out from the study, then he will be considered as a failure. Additional analyses will be conducted using logistic models to adjust for other clinical factors, such as age, hypertension, and COPD. Logistic regression will be used for the primary endpoint ($y = 1$ if a composite outcome, otherwise $y = 0$) analysis with the treatment group as the testing factor (x). The following covariates will be included in the model: age (z_1), hypertension (z_2), and COPD (z_3), site (z_4). Given the composite outcome probability $p = p(y = 1|x, z_1, z_2, z_3)$, the basic model is defined as follows:

$$\text{Logit}(p) = \ln\left(\frac{p}{1-p}\right) = \beta_0 + \beta_1 x + \beta_2 z_1 + \beta_3 z_2 + \beta_4 z_3$$

Odds ratio and 95% confidence interval (CI) will be presented using SAS PROC GENMOD or PROC LOGSTIC. If the coefficient for treatment effect is significant, then

the null hypothesis will be rejected. Logistic models will be tested for goodness of fit. We will assess goodness-of-fit using the statistic -2 log likelihood, which has a χ^2 distribution under the null hypothesis that all the explanatory variables in the model are zero. We will also consider the Akaike Information Criterion statistic and the Schwartz Criterion statistic, both of which adjust the -2-log likelihood for the number of items in the model. Models that show lack of fit will be reconsidered for the inclusion of additional variables or use of alternate models with assumptions that are better met by the study data. One alternate model if model fit is poor for logistic regression is a log-linear model.

Further, Cochran Mantel-Haenszel method will be used to adjust for three randomization stratification factors (Age: <65 vs. \geq 65, History of hypertension: yes vs. no, and Influenza severity scale: 3 vs 4/5) using SAS PROC FREQ as one of the sensitivity analyses for the primary efficacy endpoint.

Secondary Endpoint Analyses

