Subject disposition will be summarized for the ITT population. The number and percentage of patients who completed or discontinued prematurely from the study by the treatment group will be tabulated and tested using Pearson χ^2 test. The number and percentage of patients who discontinued for each reason will be presented for each intervention group. The number and percentage of patients who completed or discontinued prematurely in each intervention group will also be displayed graphically.

Adherence

Patients who change the treatment groups after randomization or have protocol violations will be identified as non-adherence to the treatment. The number and percentage of non-adherence patients will be summarized by the treatment group and tested using Pearson χ^2 test.

Site Effect

Site effect will be evaluated for four participating sites. Balances of the treatment of assignment and the primary and secondary outcomes will be assessed among the four sites. If there is significant associations between the site and treatment assignment and a study outcome at significance level of 0.05 without multiplicity adjustment, the site effect will be adjusted in the corresponding the primary or any secondary outcome along with the other prognostic factors described in the primary and secondary analyses.

Table 3: Summary of Data Analysis Plan

Endpoint Analyses	Statistical Methods	SAS Procedures
Primary Endpoint A composite endpoint of mortality, hospital stay rate, and ECMO or mechanical intubation at 15 days after randomization	Pearson Chi-square tests or Fisher exact tests Logistic regression adjusted for Age, Hypertension, and COPD	1. PROC FREQ PROC LOGISTC

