## **3.6 Concomitant Medications**

Summaries for prior and concomitant medications will be done for the ITT population. Concomitant medications will be reported at screening, day 8,15,22, and 30. Each summary below will be done for each treatment group and for all participants:

- Prior medications – medications taken prior to the study drug administration
- Concomitant medications –medications taken on or after the study drug administration

All medications recorded on the CRF will be coded to the therapeutic drug classes and generic drug names using the World Health Organization (WHO) drug classifications. The current version of the WHO drug dictionary will be used for the coding of medications.

The number and percentage of participants who take medications that are coded to each generic drug name and therapeutic drug class will be tabulated by the treatment group and tested based on Pearson  $\chi^2$  test using SAS PROC FREQ (Tables 3.6.1-2). If there are significant differences between the two treatment groups for certain study related drugs, these concomitant medication use will be adjusted for the endpoint efficacy analyses when it is necessary.

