#### 3.7.1. Primary Endpoint Analysis

The primary study endpoint will be the composite outcome of mortality, ongoing need for hospitalization, and ECMO or mechanical intubation at 15 days after randomization. This outcome will be compared according to assigned treatment groups, using Pearson  $\chi^2$  test. The test for differences between the treatment groups in the primary outcome will be conducted at an overall  $\alpha$ -level of 0.05 (i.e.  $\alpha = 0.006$  for mid-term interim analysis,  $\alpha = 0.044$  for the final analysis). If a participant drops out from the study, then he will be considered as a failure. Additional analyses will be conducted using logistic models to adjust for other clinical factors, such as age, hypertension, and COPD. Logistic regression will be used for the primary endpoint ( $y = 1$  if a composite outcome, otherwise  $y = 0$ ) analysis with the treatment group as the testing factor ( $x$ ). The following covariates will be included in the model: age ( $z_1$ ), hypertension ( $z_2$ ), and COPD ( $z_3$ ). Given the composite outcome probability  $p = p(y = 1|x, z_1, z_2, z_3)$ , the basic model is defined as follows:

$$\text{Logit}(p) = \ln\left(\frac{p}{1-p}\right) = \beta_0 + \beta_1 x + \beta_2 z_1 + \beta_3 z_2 + \beta_4 z_3$$

Odds ratio and 95% confidence interval (CI) will be presented using SAS PROC GENMOD or PROC LOGSTIC. If the coefficient for treatment effect is significant, then the null hypothesis will be rejected. Logistic models will be tested for goodness of fit. We will assess goodness-of-fit using the statistic -2 log likelihood, which has a  $\chi^2$

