#### **3.7.4 Site Effect Analysis**

Site effect will be evaluated for four participating sites. Balances of the treatment of assignment and the primary and secondary outcomes will be assessed among the four sites (Table 3.7.4.1). If there are significant associations between the site and treatment assignment and a study outcome at significance level of 0.05 without multiplicity adjustment, the site effect will be adjusted in the corresponding the primary or any secondary outcome along with the other prognostic factors described in the primary and secondary analyses.

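### Pearson is named as the primary test, but an adjusted logistic model is also allowed to reject the null with no alpha or tie-break; at the interim look a 95% interval would take type I error to about 8%

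*SAP*

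**What the plan says.** **Primary comparison.** Protocol section 10 (Primary Endpoint Analysis) and SAP 3.7.1 compare the Day 15 composite between assigned groups by Pearson chi-square and attach 0.006 (interim) and 0.044 (final) to that comparison. The logistic models come next, as a lesser item: "Additional analyses will be conducted using logistic models to adjust for other clinical factors, such as age, hypertension, and COPD". Only the Cochran-Mantel-Haenszel test is called a sensitivity analysis.

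**Second rejection rule.** Each document then gives the logistic model a rejection rule. The protocol's begins "If the coefficient for treatment effect is significant, then" and ends with the null being rejected; SAP 3.7.1 has the same sentence. Later in SAP 3.7.1, and again in SAP 3.9, significance is defined through the interval: if "the confidence interval for the odds ratio does not include 1), then the null hypothesis will be rejected". The only interval level given is in SAP 3.7.1: "Odds ratio and 95% confidence interval (CI) will be presented using SAS PROC GENMOD or PROC LOGSTIC". SAP 3.9 gives none and refers back to 3.7.1.

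**Stopping.** Under SAP 3.9 the null "can be rejected with a boundary value of 2.77", or accepted when Z lies within 0.44 of zero. The termination recommendation rests on these boundaries alone.

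**Other loose ends.** For the primary endpoint, protocol Table 3 and SAP Appendix 5.6 list "Pearson Chi-square tests or Fisher exact tests" with no rule for choosing. SAP 3.7.4 says that, after significance tests on site, "the site effect will be adjusted in the corresponding the primary or any secondary outcome"; the protocol's Site Effect text agrees. SAP 3.6 says of imbalanced drugs that "these concomitant medication use will be adjusted for the endpoint efficacy analyses when it is necessary". The protocol lists site as a model covariate but leaves it out of the formula.

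**The concern.** The protocol's Data Analysis Plan defines the primary null as an odds ratio of one, so a sentence saying the null is rejected on the logistic odds ratio speaks to the primary hypothesis. If Pearson and logistic disagree, the text supports both a positive and a negative primary result, and the choice would be made with the data in view.

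The interim is the sharpest case. If the interval in SAP 3.9 is read as the 95% interval of 3.7.1, the plan can call the null rejected at about p<0.05 while its own boundary, two-sided p=0.0056, says continue. The overall 0.05 would then not hold.

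**Working it through.** **1. The plan's own figures.** Inputs: 60% vs 35% events, described as a 42% reduction (0.60 x 0.58 = 0.348); 2:1 allocation; 90% power; two-sided 0.05; interim at 99 of 198; bounds 2.77 and 0.44; levels 0.006 and 0.044 (protocol section 10; SAP 2.6, 3.7.1, 3.9).
- Two-sided p for 2.77 is 2[1-Φ(2.77)] = 0.0056, stated as 0.006; 0.006 + 0.044 = 0.05.
- Placebo n = {z(α/2)√[p̄(1-p̄)(1+1/2)] + z(β)√[p0(1-p0) + p1(1-p1)/2]}² / (p0-p1)², with p̄ = (p0+2p1)/3. For 0.60 vs 0.348 at α=0.044 this is 61.97, so 62 + 124 = 186, as stated. For 0.60 vs 0.35 at α=0.05 it is 60.95, so 61 + 122 = 183.
- Attrition: 124/0.95 = 130.5 and 62/0.95 = 65.3, so 131 and 66; keeping 2:1 gives 132 + 66 = 198.

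**2. Type I error by reading.** With information fraction 0.5, Z2 = √½·Z1 + √½·W, where W is an independent standard normal. For bounds c1 and c2,

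α = 2[1-Φ(c1)] + ∫ φ(z){1-Φ((c2-√½z)/√½) + Φ((-c2-√½z)/√½)} dz,

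integrated over |z| ≤ c1 (futility ignored) or 0.44 < |z| ≤ c1 (futility obeyed).

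| Deciding rule | c1 | c2 | Ignored | Obeyed |
|---|---|---|---|---|
| Pearson as stated | 2.77 | 2.014 | 4.6% | 4.4% |
| 95% CI at the final look only | 2.77 | 1.960 | 5.2% | 5.0% |
| 95% CI at the interim, 0.044 at the end | 1.960 | 2.014 | 7.8% | 7.6% |
| 95% CI at both looks | 1.960 | 1.960 | 8.3% | 8.1% |

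Moving only the interim bound from 2.77 to 1.96 adds 3.2 points (7.8 - 4.6). Moving only the final bound adds 0.6 (5.2 - 4.6).

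**3. If either test may reject.** This depends on how prognostic the covariates are, which the documents do not give. Simulation used the planned stratification (age, hypertension, severity) with random blocks of 3 and 6, and 60,000 null trials per setting at a 60% event rate. Assumed prevalences: hypertension 60%, COPD 20%, severity 4/5 70%. Assumed log odds ratios for age per SD, hypertension, COPD and severity: none; 0.5/0.4/0.5/0.5; 1.0/0.8/1.0/1.0. Ranges cover these settings and futility ignored or obeyed.
- Pearson alone: 2.9-4.8%.
- Either test at matched levels: 4.4-5.2%.
- Either test, 95% CI at the final look only: 4.8-5.6%.
- Either test, 95% CI at both looks: 7.7-8.7%.
- Either test, 95% CI at the interim and 0.044 at the end: 7.3-8.3% (same model, 20,000 null trials per setting).

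**4. How often the rules conflict.** At the interim, the 95% interval excludes 1 with |Z| ≤ 2.77 in 4.3-4.6% of null trials and 32-40% at the design effect (5% dropout counted as failure). If the interim interval is matched to 2.77, this falls to 0.05-0.2% and 1-8%. At the final look, the 95% interval rejects and Pearson at 0.044 does not in 0.7-2.1% and 1.4-5.1%.

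**5. Fisher.** By exact enumeration at the final look, Pearson rejects and Fisher does not in 1.05% of null trials and 3.0-3.3% at the design effect; the reverse never occurs. With 5% dropout, using Fisher at both looks gives power of 84.2/85.1% against 87.0/88.2% for Pearson (futility obeyed/ignored). The smallest expected null cell is 33 x 0.4 = 13.2 at the interim and 66 x 0.4 = 26.4 at the end, so sparse cells are no reason to switch.

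**6. ITT power (separate point).** The protocol (Analysis Populations) and SAP 3.3 state 90% power in the ITT population, where dropouts count as failures. With unrecovered dropout d, event rates become 0.60+0.40d and 0.35+0.65d; at d=0.05 these are 0.62 and 0.3825. Exact two-stage enumeration (66/33, then 132/66) at 2.77 and 0.044, futility obeyed/ignored:
- d=0: 90.6/91.6%
- d=1%: 90.0/91.0%
- d=2%: 89.3/90.4%
- d=5%: 87.0/88.2%

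**The case against.** The best defence is that the intent is clear. Pearson is named, carries the alpha split and drives the stopping boundary, while the logistic models are introduced as additional. Near-identical rejection wording follows the Cox models for secondary endpoints, so it may be boilerplate on reading a coefficient. SAP 3.1.2 also ranks specific sections above its general 0.05.

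Much of this stands. A reader might infer that the plan never says which test is primary; the documents do not support that. A reader might also infer that the trial could stop on the logistic interval. It could not: the interim interval sentence concerns rejecting the null, not stopping. The 32-40% interim conflict mainly reflects that p<0.05 is easier to meet than p<0.0056. Site adjustment is made alongside the other prognostic factors, which places it in the regression and not in the Pearson test.

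What does not stand is that the label cures the wording. An additional analysis that rejects the primary null is not merely supportive. The precedence rule does not help, because both rejection rules sit in the same specific sections and no specific alpha exists for the logistic one.

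**Conclusion.** The concern holds as a wording defect with one material consequence. Pearson is in effect the deciding test, but a second test is given power to reject without an alpha or a tie-break. If the interim interval is read as 95%, overall type I error is about 8% (7.8/7.6% when it counts at the interim alone). On the other readings it stays near 5%. SAP 3.9 gives no level, so the 95% reading is available but not forced. The normal-theory figures need only the stated bounds and the half-way interim; the either-test and conflict figures also rest on the assumed covariate effects and prevalences.

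Three stronger readings should be resisted.
- Inflation to about 8% does not require a 95% interval at both looks; the interim alone produces it.
- Either-test error of 6-7% at matched levels, or 9-10% with 95% intervals at both looks, appears only in simulations that omit the planned stratification.
- The 90% power does not fail because of the alpha split or the futility stop. With both applied and no dropout it is 90.6%. Nor is it established that they were ignored: 186 follows from a fixed design at 0.044, as shown above. Only counting dropouts as failures takes power below 90%, and 5% unrecovered is a worst case, since both documents plan to recover missed data from patient records and VA databases.

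Fisher cannot inflate error; leaving it open costs about 3 points of power if it is chosen.

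**What to change.** - Delete the logistic rejection sentences in protocol section 10 (Primary Endpoint Analysis), SAP 3.7.1 (both places) and SAP 3.9.
- State that Pearson chi-square, with |Z|>2.77 at the interim and two-sided 0.044 at the end, is the only deciding test for the primary endpoint.
- Label the logistic, Cochran-Mantel-Haenszel and any site- or medication-adjusted analyses as supportive, with descriptive intervals.
- For consistency with the body text, remove the Fisher option for the primary endpoint from protocol Table 3 and SAP Appendix 5.6.
- Separate minor edit: in the protocol's Analysis Populations text and SAP 3.3, state ITT power as about 87-92%, depending on unrecovered dropout counted as failure.

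The cost is wording in two documents and one restated power figure. No patients or data are added, and N=198 and the 0.044 final level are unchanged.
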